2.4.7. Additional endpoints

The additional observations will be performed on the ITT population and will include:

- Proportion of subjects with early recurrence of atrial fibrillation (ERAF) by 90 days after the initial study ablation.
- Time to Therapeutic Failure
- Proportion of all ablated pulmonary veins that are isolated at the Index Procedure using the study device.
- Proportion of all ablated pulmonary veins isolated using the study device during the Index Procedure that remain isolated at the 75-day Remapping Procedure.
- The proportion of attempted subjects that achieve Chronic CTI Success, defined as persistent bi-directional electrical block across the CTI as assessed at the 75-day remapping procedure.
- The proportion of attempted subjects that achieve Chronic Focal Success, defined as persistent electrical nonconductivity of extra-PV tissue targeted for ablation in the Index Procedure, excluding the CTI

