Reproduction and distribution of this document, in whole or in part, is strictly forbidden without prior authorization from ICON PLC.

	STATISTICAL ANALYSIS PLAN	FARAPULSE PersAFOne SAP V1.0 PERSAFONE Page 20 /49
---	----------------------------------	--

ELSE IF Pacemaker, Implantable Cardioverter Defibrillator or Cardiac Resynchronization therapy device ='No' in **Patient eligibility Form (IE)** **THEN** Permanent pacemaker or ICD='No'

Index Procedure:

- Derived criteria "Procedure time (hours)" will be defined as follows:
Procedure end- Procedure start in **Procedural data form (PR)**.
- Derived criteria "FARAWAVE dwell time (hours)" will be defined as follows:
SUM of [(FARAWAVE ablation catheter remove 1 – FARAWAVE ablation catheter introduction 1), (FARAWAVE ablation catheter remove n – FARAWAVE ablation catheter introduction n)] in **Procedural data form (PR)**
- Derived criteria "PVI ablation time (hours)" will be defined as follows:
Last PVI ablation time - First PVI ablation time in **Procedural data form (AB)**
- Derived criteria "CTI (FARAFLEX) dwell time (hours)" will be defined as follows:
SUM of [(FARAFLEX ablation catheter remove 1 – FARAFLEX ablation catheter introduction 1), (FARAFLEX ablation catheter remove n – FARAFLEX ablation catheter introduction n)] in **Procedural data form (PR)**
- Derived criteria "LAPW ablation time (hours)" will be defined as follows:
Last LAPW ablation time - First LAPW ablation time in **Procedural data form (AB)**
- Derived criteria "Total number of PVI applications" will be defined as follows:
SUM of [(Count (Ablation location **IN** ("Left superior", "Left inferior", "Right superior", "Right inferior", "Right middle", "Left common ostium") **OR** (Ablation location='Other' **AND** Ablation location, Other specify='LCPV')))] in **Procedural data form (AB)**
- Derived criteria "Number of LAPW applications" will be defined as follows:
SUM of [(Count (Ablation location='Other' **AND** Ablation location, Other specify **IN** ("LA PW", "LAPW", "LEFT ATRIAL POSTERIOR WALL")))] in **Procedural data form (AB)**
- Derived criteria "Total number of CTI applications" will be defined as follows:
SUM of [(Count (Ablation location=" CTI"))] in **Procedural data form (AB)**
- Derived criteria "Total number of veins treated" will be defined as follows:

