IF Anatomical Structure/Area other specification 1 **IN** ("POSTERIOR WALL" "LA POSTERIOR WALL" "LAPW" "PA WALL" "BOX POSTERIOR WALL") **AND** Other 1 Lesion durable = 'yes' **OR** Anatomical Structure/Area other specification 2 **IN** ("POSTERIOR WALL" "LA POSTERIOR WALL" "LAPW" "PA WALL" "BOX POSTERIOR WALL") **AND** Other 2 Lesion durable = 'Yes' in **Follow-up 3D electroanatomical mapping form (RM)** **THEN** LAPW chronic isolation= 'Yes'
ELSE LAPW chronic isolation = 'No'
- Derived criteria "Number of veins durably isolated" will be defined as follows:
SUM of [LSPV chronic isolation='Yes', LIPV chronic isolation='Yes', LCPV chronic isolation='Yes', RSPV chronic isolation='Yes', RIPV chronic isolation='Yes', RMPV chronic isolation ='Yes'] in **Follow-up 3D electroanatomical mapping form (RM)**
- Derived criteria "Number of veins with gaps" will be defined as follows:
SUM of [LSPV chronic isolation='No', LIPV chronic isolation=' No', LCPV chronic isolation=' No', RSPV chronic isolation=' No', RIPV chronic isolation=' No', RMPV Chronic isolation = 'No'] in **Follow-up 3D electroanatomical mapping form (RM)**

6 and 12 Months follow up

- Derived criteria "TTM compliance (%) (calculated)" will be defined as follows:
(TTM weeks received /TTM weeks expected) *100 in **MDT excel file**
- Derived criteria "Holter compliance (%) at 6 months" will be defined as follows:

CONFIDENTIEL / CONFIDENTIAL

Toute reproduction ou distribution, totale ou partielle, de ce document, sans autorisation préalable de ICON PLC est interdite.
Reproduction and distribution of this document, in whole or in part, is strictly forbidden without prior authorization from ICON PLC.

	STATISTICAL ANALYSIS PLAN	FARAPULSE PersAFOne SAP V1.0 PERSAFONE Page 22 /49
---	----------------------------------	--

IF 6mo Holter in ('AF', 'none', 'SVT') in **MDT excel file** **THEN** Holter compliance (%) at 6 months = 'Yes'

ELSE IF 6mo Holter in ('MISSING') in **MDT excel file** **THEN** Holter compliance (%) at 6 months='No'

- Derived criteria "Holter compliance (%) at 12 months" will be defined as follows:

IF 12mo Holter in ('AF', 'none', 'SVT') in **MDT excel file** **THEN** Holter compliance (%) at 12 months = 'Yes'

ELSE IF 12mo Holter in ('MISSING') in **MDT excel file** **THEN** Holter compliance (%) at 12 months='No'

- Derived criteria "Freedom from AF/AFL/AT" will be defined as follows:

IF AF/AFL/AT status =0 in **MDT excel file** **THEN** Freedom from AF/AFL/AT ='Yes'

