COUNT of [(Left Superior Isolated/Blocked ='Yes', Left Inferior Isolated/Blocked='Yes', Left Common Ostium Isolated/Blocked='Yes', Right Middle Isolated/Blocked='Yes', Right Superior Isolated/Blocked='Yes', Right Inferior Isolated/Blocked='Yes')] / COUNT of [(Left Superior Isolated/Blocked in (Yes, No) , Left Inferior Isolated/Blocked in (Yes, No), Left Common Ostium Isolated/Blocked in (Yes, No), Right Middle Isolated/Blocked in (Yes, No), Right Superior Isolated/Blocked in (Yes, No), Right Inferior Isolated/Blocked in (Yes, No))] **in Procedural data form (PR)**
- Derived criteria "Proportion of all ablated pulmonary veins isolated using the study device during the Index Procedure that remain isolated at the 75-day remapping procedure" will be defined as follows:
(Derived criteria "Total number of veins isolated" - Derived criteria "Number of veins with gaps")/ Derived criteria "Total number of veins isolated"
- Derived criteria Proportion "Chronic CTI at 75d remap" will be defined as follows:
IF CTI lesion durable ='Yes' **in Follow-up 3D electroanatomical mapping form (RM)** **THEN** Chronic CTI at 75d remap ='Yes'
ELSE IF CTI lesion durable ='No' **in Follow-up 3D electroanatomical mapping form (RM)** **THEN** Chronic CTI at 75d remap ='No'
- Derived criteria Proportion "LAPW chronic isolation" will be defined as follows:
IF Anatomical Structure/Area other specification 1 **IN** ("POSTERIOR WALL" "LA POSTERIOR WALL" "LAPW" "PA WALL" "BOX POSTERIOR WALL") **AND** Other 1 Lesion durable = 'yes' **OR** Anatomical Structure/Area other specification 2 **IN** ("POSTERIOR WALL" "LA POSTERIOR WALL" "LAPW" "PA WALL" "BOX POSTERIOR WALL") **AND** Other 2 Lesion durable = ='Yes' **in Follow-up 3D electroanatomical mapping form (RM)** **THEN** LAPW chronic isolation= 'Yes'

CONFIDENTIEL / CONFIDENTIAL

Toute reproduction ou distribution, totale ou partielle, de ce document, sans autorisation préalable de ICON PLC est interdite.
Reproduction and distribution of this document, in whole or in part, is strictly forbidden without prior authorization from ICON PLC.

	STATISTICAL ANALYSIS PLAN	FARAPULSE PersAFOne SAP V1.0 PERSAFONE Page 26 /49
---	----------------------------------	--

ELSE LAPW chronic isolation = 'No'

Primary Safety endpoint

Unless otherwise indicated, all the following variables will be derived from the Adverse event adjudication form (CE)

- Derived criteria "Death" will be defined as follows:

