4.1.11. Table 11. Additional Endpoints

ITT Population		
N = XX		
	Mean±S.D.	
	Median (min, max) (Q1, Q3)	[95% CI]
Time to Therapeutic Failure (days)	XX±X XX (XX, XX) (XX, XX)	[XX - XX]
	n/N (%)	[95% CI]
Proportion of subjects with Early recurrence of atrial fibrillation (ERAF) by 90 days after the index procedure	XX/XX (XX.X%)	[XX% - XX%]
Proportion of all ablated pulmonary veins that are isolated at the Index Procedure using the study device	XX/XX (XX.X%)	[XX% - XX%]
Proportion of all ablated pulmonary veins isolated using the study device during the Index Procedure that remain isolated at the 75-day remapping procedure	XX/XX (XX.X%)	[XX% - XX%]

CONFIDENTIEL / CONFIDENTIAL

Toute reproduction ou distribution, totale ou partielle, de ce document, sans autorisation préalable de ICON PLC est interdite.
Reproduction and distribution of this document, in whole or in part, is strictly forbidden without prior authorization from ICON PLC.

	STATISTICAL ANALYSIS PLAN	FARAPULSE PersAFOne SAP V1.0 PERSAFONE Page 42 /49
---	----------------------------------	--

The proportion of attempted subjects that achieve Chronic CTI Success, defined as persistent bi-directional electrical block across the CTI assessed at the 75-day Remapping Procedure	XX/XX (XX.X%)	[XX% - XX%]
The proportion of attempted subjects that achieve Chronic Focal Success, defined as persistent electrical nonconductivity of all extra-PV tissue targeted for ablation in the Index Procedure, excluding the CTI	XX/XX (XX.X%)	[XX% - XX%]

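### SAP 2.5 gives no valid derivation of Chronic Focal Success; the only candidate is a posterior-wall rule whose default 'No' conflicts with the SAP's own missing-item rule

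*SAP*

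**What the plan says.** The protocol synopsis (Additional Assessments), Protocol 6.5, SAP 2.4.7 and SAP Table 11 all define Chronic Focal Success among attempted subjects, over extra-PV tissue targeted at index, with the CTI excluded. The Table 11 row reads "persistent electrical nonconductivity of all extra-PV tissue targeted for ablation in the Index Procedure, excluding the CTI". The word 'all' stands in the synopsis and Table 11 but not in Protocol 6.5 or SAP 2.4.7.

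SAP 2.5 contains no item called Chronic Focal Success. Its additional-endpoints block ends with an item called LAPW chronic isolation, which repeats the rule given earlier in 2.5 under the 75-day remap. The rule scores 'Yes' if either of two free-text 'Other' fields on the remap form matches one of five strings (such as "BOX POSTERIOR WALL") and that lesion is durable. Everything else falls to "ELSE LAPW chronic isolation = 'No".

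Three other provisions bear on this:
- SAP 2.5 opens by making a derived criterion missing if any item needed to calculate it is missing.
- SAP 2.1.3 calculates percentages on non-missing observations.
- The index rule for the number of LAPW applications uses a different list of three strings, one of which is "LEFT ATRIAL POSTERIOR WALL".

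**The concern.** A programmer working from SAP 2.5 has nothing to implement for the Table 11 row except the LAPW rule. That rule differs from the definition in its lesion set (posterior wall only) and its eligible subjects (no attempted or remapped condition). Its default branch also turns anything unmatched into a failure.

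Both conditions matter. Extra-PV ablation is at the investigator's discretion (protocol synopsis, Planned Procedure), and Protocol 3.12.5 provides for patients who decline the remap. Assessing FARAFLEX for focal ablation is one of the study's listed aims (Protocol 1.4), so a misreported focal durability rate would mislead the design of later studies.

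**Working it through.** **1. Is there a derivation?** The last four rows of Table 11 are veins isolated at index, veins still isolated at remap, Chronic CTI and Chronic Focal. The four additional-endpoint derivations in SAP 2.5 run in the same order, with LAPW chronic isolation in fourth place. Table 11 has no LAPW row. The link is an inference from order; the SAP does not state it.

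**2. Lesion set.** The definition covers all targeted non-CTI extra-PV tissue. The LAPW rule reads only Other 1 and Other 2. The remap form also has fields for mitral isthmus, roof line and posterior line, and SAP 2.5 derives each separately under secondary feasibility. None feeds the LAPW rule.

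**3. Coding.** Chronic CTI, directly above, becomes 'No' only on a recorded 'No', so a blank stays missing. Acute CTI requires that the CTI was attempted. The LAPW rule has neither safeguard.

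**4. String lists.** Index: `LA PW`, `LAPW`, "LEFT ATRIAL POSTERIOR WALL". Remap: `POSTERIOR WALL`, `LA POSTERIOR WALL`, `LAPW`, `PA WALL`, "BOX POSTERIOR WALL". The only shared string is `LAPW`.

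**5. The default branch against the missing-item rule.** Three readings were tested. Literal: the default as written. Strict: missing if any of the four fields (two site names, two durability answers) is blank. Lenient: missing only if all four are blank.

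| Case | Literal | Strict | Lenient |
|---|---|---|---|
| Not remapped | No | Missing | Missing |
| Remapped, LAPW untreated, Other fields blank | No | Missing | Missing |
| LAPW untreated, another site in Other 1, Other 2 blank | No | Missing | No |
| `LAPW` durable, Other 2 blank | Yes | Missing | Yes |
| `LA PW` durable, Other 2 blank | No | Missing | No |
| `LA PW` durable, both Other fields filled | No | No | No |
| `LAPW` durable, another site not durable | Yes | Yes | Yes |

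The last row is a failure under the definition and a success under all three readings.

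**6. Size.** The documents do not give the number treated outside the veins, so all counts below are assumed. Totals are 25 (printed in the Table 5 shell) and 40 (planned). Intervals are exact 95%.

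- *Default branch, literal reading.* 20 treated and remapped, 19 durable: 19/20 = 95.0% (75.1–99.9) by definition, but 19/25 = 76.0% (54.9–90.6) over all ITT subjects. With 30 of 30 durable among 40: 100% becomes 30/40 = 75.0% (58.8–87.3).
- *Range.* If 10 to 20 are treated and remapped and all are durable, 100% becomes 10/25 = 40.0% to 20/25 = 80.0%, or 10/40 = 25.0% to 20/40 = 50.0%.
- *Unlisted spelling.* One durable lesion unmatched: 9/10 = 90.0% to 19/20 = 95.0% instead of 100%.
- *Lesion set, upward.* 20 attempted and remapped, all with a durable posterior wall, 2 with a failed roof or mitral line: 18/20 = 90.0% (68.3–98.8) by definition, but 20/20 = 100% (83.2–100) by the LAPW rule, even with the right denominator.

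**The case against.** A reader might infer four stronger things that the documents do not support.

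- *That the SAP programs Chronic Focal Success as posterior-wall isolation.* It never says so. The item keeps its own name and has its own row in Table 5. Two other Table 11 rows, time to therapeutic failure and early recurrence, also lack a derivation in that block, so an omission is plausible. If the link is rejected, Chronic Focal Success has no derivation at all, and the remedy is the same.
- *That un-remapped and untreated subjects are certainly scored as failures.* The missing-item rule, with percentages on non-missing observations, may remove those with blank fields from the denominator. This objection stands, but the SAP does not say which rule prevails. The strict reading also drops true successes whose second Other field is blank. The lenient reading still fails an untreated subject who has another site recorded.
- *That the mismatch between lists itself creates failures.* The index list only feeds an application count from a different form. The mismatch shows which spellings the SAP expects; a lesion is misclassified only if such a spelling appears on the remap form.
- *That the bias is downward.* The default branch pushes down and the narrow lesion set pushes up. The net direction is unknown.

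It is also fair to say that the other extra-PV lesions are not wholly left out. Their durability is derived separately and reported in Table 13. What is missing is the combined per-subject endpoint.

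**Conclusion.** The point holds in this form: Chronic Focal Success has no valid derivation, and the one rule that could fill its place does not deliver the defined endpoint under any reading of the default branch and the missing-item rule. That conclusion rests on the text alone.

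The size is not known. The percentages depend on assumed numbers treated, remapped and durable. The downward figures of 76.0% and 75.0% also depend on the literal default applied to every ITT subject, and would shrink or vanish where the missing-item rule removes those subjects.

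This is an additional assessment in a descriptive study without hypothesis tests. It should be corrected before analysis, but it does not touch the primary endpoints.

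**What to change.** In SAP 2.5:

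1. Add a derivation named Chronic Focal Success, covering every non-CTI extra-PV site targeted at index, among subjects attempted and remapped. Score 'Yes' if all such sites are durable, 'No' if any is recorded as not durable, otherwise missing. Report the number attempted but not remapped. Use the word 'all' consistently in the definition.
2. In the LAPW rule, replace the unconditional default with an explicit 'No' condition, as the CTI rule already has.
3. State that unused Other fields are not needed items under the missing-item rule.
4. Code free-text sites to one dictionary (LAPW, roof line, mitral isthmus, posterior line, other) for both index and remap, fixed before durability is tabulated.
5. Give the LAPW row of Table 5 its own denominator: subjects with LAPW ablation at index who were remapped. The focal denominator would be wrong there, because it would bring in roof-only or mitral-only subjects.

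The cost is SAP wording, one recoding table and a program change. The derivations already in SAP 2.5 show that the forms record index ablation location and lesion durability at remap.
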